4.1.2 Exclusion Criteria (interventional phase)

1) Pregnancy;

- 2) Expected death or withdrawal of life-sustaining treatments within 48 hours;
- 3) Previously enrolled in this study;
- 4) Formal indication for corticosteroids according to most recent international guidelines
- 5) Vaccination with live virus within past 6 months
- 6) Hypersensitivity to hydrocortisone or fludrocortisone or any of their excipients (SPC)
- 7) Women of childbearing potential not using contraception
- 8) Nursing women

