	e. Transcriptomic SRS2
	f. Endotype B
	g. PCR COVID-19
	h. PCR Influenza
	i. PCR other respiratory virus
	6. Affiliation to a social security system or to an universal health
	coverage (Couverture Maladie Universelle, CMU).
	7. Patients under guardianship or curatorship will be included.
	8. Patients in case of simple emergency (legal definition) will be
	included.
	9. Patients managed with covid 19 and having biological
	samples available
Exclusion Criteria	1. Pregnancy;
observational	2. Expected death or withdrawal of life-sustaining treatments within 48 hours;
phase: (N°1,2,3)	3. Previously enrolled in this study
interventional	4. Formal indication for corticosteroids according to most recent
phase:	international guidelines
(N°:1,2,3,4,5,6,7,8).	5. Vaccination with live virus within past 6 months
(11,1,2,0,4,0,0,7,0).	6. Hypersensitivity to hydrocortisone or fludrocortisone or any of their
	excipients (spc)
	7. Women of childbearing potential not using contraception
	8. Nursing women
Study Intervention	-Observational phase (run-in period): additional biological samples
	For the restrospective part (Covid patients): telephone
	follow-up -Interventional phase:
	Investigational products or their placebo will be administered to
	patients on the basis of RECORDS signatures
	Investigational products included:
	- Hydrocortisone hemisuccinate 50 mg: one intravenous injection
	every 6 hours, and
	- 9 alpha fludrocortisone 50 µg: one tablet per day via a nasogastric
	tube.
	All treatments will be stopped after 7 days or until the patient has left the intensive care unit (whichever occurs first) without tapering off.
Randomization	Web-based randomization system available 24/7. Eligible patients will
(Interventional	be randomized in a 1:1 ratio to corticoseroids or matching placebo.
phase)	We will use permuted blocks of undisclosed and variable size and
	stratify randomization by site and biomarkers.
Sample Size	We will enroll a total of at most 1800 patients in this adaptative trial.
	Sites are expected to enroll at least 1 or 2 patients per month. By
	enrolling 376 evaluable patients per arm, the study will have 80%
	power to detect a 10% absolute risk reduction (from 45% to 35%, which
Study duration	corresponds to a 20% relative risk reduction). Inclusion period: 48 months:
Study duration	Treatment 7 days and follow-up: 6 months.Daily during ICU stay and
	telephone follow-up at 6 months.
	Total study period: 54 months
L	

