4.1.1.1.2 Exclusion Criteria (observational phase)

- Pregnancy;
- Expected death or withdrawal of life-sustaining treatments within 48 hours;
- Previously enrolled in this study

The observational phase poses no risk to participants. Any adverse reactions observed in the patients during this phase are reported by the investigators as per the local vigilance procedures. All adverse events will be recorded in the patient case report form (eCRF).

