5) **Endotype B cohort**: as defined by endotyping of 100 genes reflecting adaptive immunitiy and glucocorticoid receptor signalling. This approach in children with sepsis identified two distinct endotypes A and B. Endotype A was characterized by repression of the majority of these genes (Wong 2011).

Patients presenting with an endotype A have a profile of immune suppression, and were at higher risk for mortality. Nevertheless, those patients with an endotype A at ICU day 1 that shifted for an endotype B later on draw benefit from corticosteroids (Wong 2018).

6) *PCR COVID-19 cohort*: the emergence in the end of 2019, of a novel coronavirus, SARS-CoV-2, related disease, places a major burden on worll health care systems. The disease is characterized by viral sepsis with a key role of over-activation of the complement system and inflammatory mediators. Corticosteroids have been provent to reduce mortality at 28-day (RECOVERY 2020; Sterne 2020) The phenotype COVID-19 may identify among patients with sepsis those who may be benefit from corticosteroids. In this biomarker cohort, all patients will receive dexamethasone 6 mg per day for 10 days and will be assigned to fludrocortisone or its placebo. Indeed, dexamethasone has no mineralocorticoid activity. The added value of mineralocorticoid is worth being evaluated owing to the role of angiotensin-converting enzyme 2 receptor and endothelial dysfunction in the pathogenesis of COVID-19.

7) **PCR Influenza cohort**: seasonal influenza causes yearly thousands of death primarily by pneumonia related sepsis. While retrospective observational studies reported controversial effects of corticosteroids in these patients, there are still no high quality randomized trial to inform routine practice.

8) *PCR other respiratory viruses cohort*: likewise, seasonal non-influenza viral pneumonia causes thousands of death due to sepsis. While retrospective observational studies reported controversial effects of corticosteroids in these patients, there are still no high quality randomized trial to inform routine practice.

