4.5 Randomization Methods

4.5.1 Allocation sequence generation

[figure not shown]
A computer process will be used to generate allocation sequences in a 1:1. Any evidence suggesting increased harm in patients presenting with a contemplated biomarker will lead to the termination of recruitment of patients presenting with this biomarker and will qualify the corresponding biomarker for identifying patients who should not be treated by hydrocortisone plus fludrocortisone (see section 9). A randomization list will be generated beforehand by a computer program and verified according to the procedures of the sponsor, independently from the physicians who will recruit patients.

4.5.2 Stratification:

Randomization will be stratified on the following biomarkers:

- 1. CIRCI
- 2. Endocan
- 3. GILZ
- 4. CPD
- 5. Transcriptomic SRS2
- 6. Endotype B
- 7. COVID-19
- 8. Influenza
- 9. Other respiratory viruses

The full statistical analysis plan will be published before the first interim analyse.

According to the adaptive design of the umbrella trial, the number of biomarker strata is not fixed and will vary with 1) information gained from actual study participants on added-value of a specific biomarker, 2) from new biomarker released by RECORDS WP3-6, 3° from new relevant biomarker released in the literature that will be screened n a trimester basis throughout the study period. These novel biomarkers may include new clinical algorithm or phenotypes, new omic-derived signature, new biological biomarker issued from blood, urine or exhaled air.

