5.11.4 POSOLOGY AND DRUGS ADMINISTRATION

Initiation of treatments:

Treatment should be started immediately after randomization (day 0 of the study).

Posology:

- Hydrocortisone hemisuccinate /placebo will be given as 50 mg intravenous bolus every 6 hours

- Fludrocortisone /placebo* will be given as a 50 µg tablet via a nasogastric tube once per day in the morning

* Patients with COVID-19 will receive only experimental fludrocortisone or its placebo AND NOT hydrocortisone or its placebo as they will receive dexamethasone as the standard of care.

Duration of treatments:

Study drugs will be given until the patient will be discharge from the ICU for a maximal treatment duration of 7 days for steroids. Study drugs will be stopped without tapering off.

Reconstitution for IV injection of hydrocortisone/placebo:

Hydrocortisone hemisuccinate lyophilisate will be reconstituted prior to use with 2 mL water for injection. The solvent must be injected gently into the vial. Reconstitution and dilution should be performed in accordance with Good Clinical Practices guidelines, particularly with respect to asepsis and to Hydrocortisone SmPC. Hydrocortisone must not be used if the reconstituted solution has a cloudy appearance or contains floccular or particulate matter. The SmPC instructions for use, handling and disposal should be strictly followed.

The volume injected will be 1 mL, containing 50 mg of Hydrocortisone.

"Administration of fludrocortisone/placebo

A 50 μ g fludrocortisone/Placebo tablet is administered, enterally, once a day. For patients with a nasogastric tube, the entire tablet will be introduced into the nozzle of the tube. The tube will be flushed with 50 mL of water (the 10 first mL have to be injected slowly) and clamped for at least 30 minutes after tablet administration."

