5.12 Co-Interventions

We propose a pragmatic design whereby all co-interventions will be left to the discretion of the treating physician, who will be blinded to treatment assignment. However, we will carefully record use of relevant co-interventions. Unblinded administration of intravenous corticosteroids will constitute a protocol violation, except for patients with COVID-19.

Patients with COVID-19 will receive dexamethasone once daily at a dose of 6 mg for 10 days, as their standard of care

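### Exclusion criterion 4 has no COVID-19 exception, so it would bar the planned COVID-19 cohort if guidelines formally indicate corticosteroids for that disease

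*Protocol*

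**What the plan says.** Section 4.1.2 lists eight exclusion criteria for the interventional phase. The fourth is "Formal indication for corticosteroids according to most recent international guidelines", with nothing after it. The study summary repeats it ("Formal indication for corticosteroids according to most recent" and so on), again without qualification. The exclusion list for the observational phase, section 4.1.1.1.2, has three items and omits this one, so the rule governs only the randomised phase.

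In that same phase, inclusion criterion 5 names PCR COVID-19 among the biomarkers for which a patient may have been tested. Section 4.1.3.1, item 6, defines the cohort: "In this biomarker cohort, all patients will receive dexamethasone 6 mg per day for 10 days and will be assigned to fludrocortisone or its placebo". The same item states the evidence: "Corticosteroids have been provent to reduce mortality at 28-day". Section 4.5.2 includes COVID-19 among its nine stratification factors. Section 5.11.4 withholds hydrocortisone and its placebo from these patients "as they will receive dexamethasone as the standard of care".

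The rules on concomitant corticosteroids make room for them. Section 5.12 says "Unblinded administration of intravenous corticosteroids will constitute a protocol violation, except for patients with COVID-19". Section 5.12.1 bans other corticosteroids but exempts the COVID-19 dexamethasone course, and section 5.12.2 lists that course under authorised treatments.

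**The concern.** Criterion 4 is an entry rule, checked for each patient at the baseline visit (section 5.3). It depends on whether a guideline indication for corticosteroids exists. It does not ask which steroid is being randomised or whether the indicated steroid will be given anyway. A treatment that every patient in a cohort receives as standard of care, and that the protocol describes as proven to lower mortality, is a natural candidate for such an indication.

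If it is one, the protocol asks sites to randomise patients whom its own exclusion list rejects. Sites could then differ: some would enrol on the strength of the cohort definition, and others would decline on the strength of the criterion. Monitors check compliance with the protocol (section 10.2), and non-compliance is declared to the sponsor (section 10.4). Eligibility also matters after entry, because section 5.16 allows post-randomisation exclusion of patients randomised by mistake, subject to several further conditions.

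**Working it through.** No calculation in the protocol depends on this criterion, so the check sets the texts side by side.

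| Place in the protocol | Bearing on COVID-19 patients in the interventional phase | COVID-19 exception written as such? |
|---|---|---|
| Study summary, exclusion 4 | Guideline indication for corticosteroids excludes | No |
| Section 4.1.2, exclusion 4 | Same | No |
| Inclusion criterion 5 (summary and body) | PCR COVID-19 is a listed biomarker | Not applicable |
| Section 4.1.3.1, item 6 | Dexamethasone for all; fludrocortisone or placebo randomised | Not applicable |
| Section 4.5.2, item 7 | Randomisation stratum | Not applicable |
| Section 5.11.4 | Dexamethasone is standard of care; hydrocortisone withheld | Dosing footnote |
| Section 5.12 | Open intravenous corticosteroids are a violation | Yes |
| Section 5.12.1 | Other corticosteroids banned | Yes |
| Section 5.12.2 | Open-label dexamethasone authorised | Not applicable |

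**Counts.** Five places provide dexamethasone for COVID-19 patients in this phase: 4.1.3.1, 5.11.4, 5.12, 5.12.1 and 5.12.2. Two of them, 5.12 and 5.12.1, do so as an exception to a general rule. Criterion 4 appears twice, and neither copy carries the exception. COVID-19 is one of nine strata in 4.5.2 and one of eight cohorts in 4.1.3.1. These counts locate the conflict; they do not measure an effect.

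**Reasoning.**

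1. Criterion 4 applies to every interventional patient, because nothing in it limits it to particular cohorts.
2. It is triggered by a formal indication in current international guidelines.
3. Whether COVID-19 carries such an indication is not stated. Sections 4.1.1, 4.1.3.1 and 5.12.2 rest the dexamethasone on one trial and one meta-analysis. The guidelines discussed in section 1.4.1 concern sepsis, with septic shock poorly responsive to fluids and vasopressors as the situation in which steroids are accepted.
4. Calling dexamethasone standard of care makes a guideline indication the natural inference, but it remains an inference.
5. The criterion follows the most recent guidelines, and enrolment lasts 48 months (section 5.7). Even if no such guideline existed when the protocol was written, one issued later would trigger the exclusion with no change to the text.
6. If the trigger is met, criterion 4 and the cohort definition cannot both be followed as written.

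**The case against.** The strongest reply is that the decisive premise is missing from the document. The criterion speaks of international guidelines, and the protocol cites none for COVID-19. Standard of care and proven benefit are not the same as a formal guideline indication, and the guidelines the protocol does describe are about sepsis. This stands. A reader might infer that the COVID-19 cohort is ineligible outright, or that each randomisation into it is an eligibility deviation. The document does not support that: on its text alone, eligibility is left open.

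Second, COVID-19 is named within the eligibility section itself, under inclusion criterion 5, just before the exclusions, and the cohort, stratum and dosing provisions are specific. Most investigators would therefore enrol. This also stands as a statement of intent, which is not in doubt. It does not remove the conflict: inclusion criterion 5 asks only that a patient has been tested, and meeting an inclusion criterion does not override an exclusion.

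Third, a plausible purpose of criterion 4 is to avoid withholding an indicated steroid from the placebo arm, and here both arms receive dexamethasone. That is a fair reading of purpose, but the protocol gives no rationale for the criterion and the wording contains no such limit. Nor does it confine the exclusion to unrelated disease, such as the autoimmune example in section 5.12.1. That section states the COVID-19 exception in addition to the example, which suggests that the authors thought the exception had to be spelled out.

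**Conclusion.** The concern holds in conditional form. Criterion 4 has no COVID-19 exception in either copy. If, at any time during enrolment, international guidelines indicate corticosteroids for COVID-19, the criterion taken literally bars a cohort the protocol plans, against its clear intent. The conclusion rests on one assumption that the document does not settle, namely that such a guideline indication exists or comes to exist. The standard-of-care description makes it likely but does not establish it, so confidence is medium.

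The point is minor. It is a conflict of wording in an entry rule and implies no flaw in the design of the cohort. One of nine strata is affected, and no patient number is claimed because the protocol gives no expected COVID-19 recruitment. No effect on power, error rates or bias is claimed.

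**What to change.** Add to exclusion criterion 4, in both the study summary and section 4.1.2: *except dexamethasone given as standard of care for COVID-19*. This matches the exceptions already in sections 5.12 and 5.12.1, and it removes the dependence on what guidelines say in any given month of enrolment.

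Section 11.4.5 requires a formal amendment for a change to the inclusion or exclusion criteria, so the clause can be bundled with the next one. The cost is one clause in two places. Sample size, randomisation, data collection and analysis do not change.

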4.1.3 Biomarker-defined subgroups

To remain pragmatic, this trial has broad eligibility criteria and includes all patients admitted to the ICU with a primary diagnosis of sepsis, community acquired pneumonia or ARDS. Patients will be further characterized at the cellular and molecular levels based on biomarkers whether measured in blood, urines, intracellularly, or exhaled air and whether being proteins, cells, metabolites or genes products (see trial flow chart 4.1.19).

The RECORDS Trial is based on the assumption that patients with sepsis regardless the pathogen (bacteria or virus) and demonstrable acute proinflammatory states or altered endogenous corticosteroids activity are the more likely to benefit from corticosteroids whereas those with evidence for a depressed immune state or preserved endogenous corticosteroids activity may be harmed by the corticotherapy. Thus, we will investigate the following biomarker-defined "cohorts."

4.1.3.1 Biomarkers that are readilty available for bedside use for bedside use

1) *CIRCI "cohort"*: defined by baseline total cortisol of 10 μ g/dL or less OR a maximum increment in total cortisol of less than 9 μ g/dL at 30 and 60 minutes following a 250 μ g intravenous bolus of Synacthen (Annane et al). This biomarker is considered as the best available test for CIRCI, a syndrome of insufficient tissue activity of corticosteroids that may occur in critically ill patients like sepsis (Annane 2017a; Annane 2017b).

2) *Low plasma endocan cohort*: defined by levels of less than 2 ng/ml. This biomarker is an endothelial peptidoglycan that contribute regulating the inflammation by counteracting the leukodiapesis that is also a key target for corticosteroids (De Freitas Caires 2018; Gaudet 2017). Low circulating levels of endocan may result from insufficient release of exaggerated clearance. Then, low endocan levels may identify patients with a proinflammatory state (Gaudet 2018) that can be corrected by corticosteroids.

3) **CPD cohort**: defined by an increased circulating monocytes distribution width. Increased volume and other cell pathologic data (CPD) have been recently characterized as early index of sepsis and shown to correlate with severity and excesive systemic inflammation (Crouser 2017). This cellular biomarker has been approved by the FDA and can be very rapidly obtained as fast as the white blood cell count and on the same blood sample.

4) *Transcriptomic SRS cohort*: transcriptomic analysis of peripheral leukocytes defined two distinct sespsis response signatures SS1 and SRS2 (Davenport 2018). SRS1 is characterized by features of endotoxin tolerance, T -cell exhaustion, and downregulation of human leucocyte antigen (HLA) class II suggesting immune suppression whereas SRS2 may correspond to relative immune competency. Grouping septic patients relatively to SRS1 or SRS2 can reliably be done by using a generalized linear model based on the set of seven genes (DYRK2, CCNB1IP1, TDRD9, ZAP70, ARL14EP, MDC1, and ADGRE3). Previous work in rather small sized cohort of sepsis suggested increased mortality with hydrocortisone in SRS2 patients (Antcliffe 2018).

5) **Endotype B cohort**: as defined by endotyping of 100 genes reflecting adaptive immunitiy and glucocorticoid receptor signalling. This approach in children with sepsis identified two distinct endotypes A and B. Endotype A was characterized by repression of the majority of these genes (Wong 2011).

Patients presenting with an endotype A have a profile of immune suppression, and were at higher risk for mortality. Nevertheless, those patients with an endotype A at ICU day 1 that shifted for an endotype B later on draw benefit from corticosteroids (Wong 2018).

6) *PCR COVID-19 cohort*: the emergence in the end of 2019, of a novel coronavirus, SARS-CoV-2, related disease, places a major burden on worll health care systems. The disease is characterized by viral sepsis with a key role of over-activation of the complement system and inflammatory mediators. Corticosteroids have been provent to reduce mortality at 28-day (RECOVERY 2020; Sterne 2020) The phenotype COVID-19 may identify among patients with sepsis those who may be benefit from corticosteroids. In this biomarker cohort, all patients will receive dexamethasone 6 mg per day for 10 days and will be assigned to fludrocortisone or its placebo. Indeed, dexamethasone has no mineralocorticoid activity. The added value of mineralocorticoid is worth being evaluated owing to the role of angiotensin-converting enzyme 2 receptor and endothelial dysfunction in the pathogenesis of COVID-19.

7) **PCR Influenza cohort**: seasonal influenza causes yearly thousands of death primarily by pneumonia related sepsis. While retrospective observational studies reported controversial effects of corticosteroids in these patients, there are still no high quality randomized trial to inform routine practice.

8) *PCR other respiratory viruses cohort*: likewise, seasonal non-influenza viral pneumonia causes thousands of death due to sepsis. While retrospective observational studies reported controversial effects of corticosteroids in these patients, there are still no high quality randomized trial to inform routine practice.

4.1.3.2 Biomarkers that will be released by other groups

Knowing that other groups are currently working on similar research program, we anticipate the possibility of adapting the RECORDS trial by adding new biomarker-defined cohort whenever they will become available.

• Figure 1. Schema of the relations between the WPs and the positioning of the BRC

Version 4.0 dated 31/05/2019

4.2 RECRUITMENT STRATEGY

As per standard practice for critical care research, before any examination or act related to the study, the clinical investigator will inform the eligible person, then collect the free and written consent of the person undergoing to the research if he/she is able to consent.

Given the management of intensive care patients, we will be confronted in this study with the case of simple emergency inclusion (France art. L. 1122-1 CSP). Therefore, the clinical investigator may include a patient without his or her written consent but with the written consent of his or her family members or the person of trust if they are present. The participant will be informed as soon as possible to consent to the continuation of the research (deferred consent).

Given the context, patients under guardianship or curatorship will be included. The consent of the guardian/curator will be sought, as well as the patient (

Once the consents are obtained, for both stages (the run-in observational and the interventional periods) participants samples will be used for the cellular and molecular testings. At the second stage (interventional period), consenting participant will be assigned to a biomarker cohort and randomized, then treatment will start immediately as per trial allocation.

We anticipate that each participating clinical site will enroll at least 1 or 2 patients per month, a conservative estimate given the experience in previous trials conducted in a similar population, by CRICS-TRIGERSEP network.

